AE=adverse event; anti-HBc=hepatitis B core antibody; BP=blood pressure; C=cycle; DNA=deoxyribonucleic acid; ECG=electrocardiogram; EORTC QLQ-C30=European Organisation for Research and Treatment of Cancer Quality of Life Questionnaire Core 30; EoT=end of treatment; FLACC=Face, Legs, Activity, Cry, Consolability; HBsAg=hepatitis B surface antigen; HBV=hepatitis B virus; HCV=hepatitis C virus; NA=not applicable; NRS=Numeric Rating Scale; PCR=polymerase chain reaction; PedsQL=Paediatric Quality of Life Inventory; PGIC=patient's global impression of change; PGIS=patient's global impression of severity; PII=Pain Interference Index; PK=pharmacokinetics; PlexiQoL=plexiform neurofibromas quality of life scale; PROMIS=Patient-Reported Outcomes Measurement Information System; RNA=ribonucleic acid.

^a Assessments will be performed at the end of each cycle. Selumetinib will be dispensed after all assessments have been performed and the next cycle will begin at that point.

- ^b Screening tests should be performed within 28 days before the first administration of study treatment, unless otherwise indicated.
- ^c Treatment with selumetinib may be continued until disease progression or unacceptable drug-related toxicity, whichever occurs first.
- ^d The EoT visit will be performed for subjects who permanently discontinue study treatment for any reason (except for death, lost to follow-up or withdrawal of consent).
- ^e The 30-day safety follow-up assessments will be conducted at 30 days post-last dose/EoT for both paediatric and adult cohorts.
- ^f Long-term post-treatment safety follow-up assessments will be conducted for 1 year (at 6 and 12 months post-treatment) for paediatric subjects only.
- ^g Subjects need to be hospitalised for intensive PK sampling during the single dose period (from Cycle 0 Day -1 to Cycle 0 Day 2) and on Cycle 1 Day 8. During Cycle 0, PK samples will be collected pre-dose, 30 minutes, and 1, 1.5, 3, 6, 8, 12, 24 and 30 hours post-dose. At Cycle 1 Day 8, PK sample time points will be collected pre-dose, 30 minutes, and 1.5, 3, 6, and 12 hours post-dose.
- ^h Subjects who are anti-HBc positive and who are HBsAg negative will need to have a negative HBV DNA PCR result before enrolment.
- ⁱ Subjects who are hepatitis C antibody positive will need to have a negative HCV RNA PCR result before enrolment.

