To determine the effect of selumetinib on physical functioning	 Patient-Reported Outcomes Measurement Information System (PROMIS; upper extremity; self- and parent reported- in the paediatric cohort). PROMIS (mobility; self- and parent reported- in the paediatric cohort). PROMIS Physical Function - Short Form 8c 7-day (adult cohort).
Exploratory objectives:	Endpoints:
To evaluate patient's global impression of severity (PGIS) of symptoms	• PGIS (adult cohort; self- and parent-reported in the paediatric cohort).

To evaluate patient's global impression of change (PGIC) in symptoms	•	PGIC (adult cohort; self- and parent-reported in the paediatric cohort).		
To determine the effect of selumetinib on disfigurement	•	Photographic evaluation.		
Safety objective: contained within the primary objectives.				

Overall design:

This is an open label Phase 1 study with 2 independent cohorts to assess the safety, tolerability, PK and clinical efficacy of selumetinib in Chinese paediatric and adult subjects with a clinical diagnosis of NF1 per National Institutes of Health (NIH) guidelines (NIH Consensus Development Conference Statement 1988) and inoperable measurable PNs that require treatment due to symptoms or with the potential to develop significant clinical complications. Approximately 16 paediatric and 16 adult subjects with NF1 and inoperable PN will be enrolled in the study in China. The assignment to treatment and evaluation of efficacy and safety will be performed independently for each cohort. The Safety Review Committee (SRC) will evaluate preliminary tolerability, safety and available PK data after the first 6 subjects in both cohorts have been treated for approximately 3 cycles. Additional enrolment will be initiated per SRC recommendation. Detailed information will be provided in the SRC charter.

Study period:

Estimated date of first subject enrolled: Quarter (Q)4 2020

Estimated date of last subject completed: Q4 2023

Number of subjects:

Approximately 16 paediatric and 16 adult subjects with a clinical diagnosis of NF1 and inoperable PN will be enrolled in the study to obtain adequate PK and safety data. Each subject should meet all of the inclusion criteria and none of the exclusion criteria for this study in order to be enrolled in the study.

Treatments and treatment duration:

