Following the screening period (Day -28 to Day -1), all eligible subjects will first receive a single oral dose of selumetinib 25 mg/m^2 (Cycle 0). After a period of 2 days, oral selumetinib 25 mg/m^2 twice daily (approximately every 12 hours) will be administered continuously for 28-day cycles (starting at Cycle 1) with no rest periods between cycles. Subjects should be instructed to take the dose of selumetinib on an empty stomach (no food or drink other than water for 2 hours before and 1 hour after dosing) with water only. The capsules cannot be crushed and must be swallowed whole.

CONFIDENTIAL AND PROPRIETARY 23 of 183

Dosing will be performed based on body surface area (BSA) calculated by the equation below, and doses will be rounded to the nearest 5 to 10 mg using a dosing nomogram. BSA should be calculated at screening and every tumour assessment visit. The dose of selumetinib will be capped at 50 mg when BSA is \geq 1.9 m². At follow-up evaluations during tumour assessment visits, the dose of selumetinib will be adjusted for changes in BSA according to the dosing nomogram.

*For paediatric subjects with a body weight \leq 30 kg:

BSA (m^2) = body weight (kg) × 0.035 + 0.1

*For paediatric subjects with a body weight \geq 30 kg:

BSA $(m^2) = 1.15 + (body weight [kg] - 30) \times 0.02$

For all adult subjects:

BSA $(m^2) = 0.0061 \times \text{height} (\text{cm}) + 0.0128 \times \text{body weight} (\text{kg}) - 0.01529$

*For paediatric subjects the BSA calculation was refer from China National Formulary (Chemicals and Biological Products for Children) 2013 version.

Subjects will continue to receive selumetinib until disease progression or unacceptable drug-related toxicity, whichever occurs first. All subjects will be evaluated for safety and efficacy at a regular basis, as defined in Table 1.

The 30-day safety follow-up visits will be conducted at 30 days post-last dose/end of treatment for both paediatric and adult cohorts. Long-term post-treatment safety follow-up assessments will be conducted for 1 year (at 6- and 12-months post-treatment) for paediatric subjects only.

For subjects who discontinue study treatment due to reasons other than disease progression, tumour assessments will continue for approximately 1 year, if clinically applicable, and the assessment schedule should continue per the regular tumour assessment interval.

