3. OBJECTIVES AND ENDPOINTS

Table 2Study objectives

Primary objectives:	Endpoints:	
To assess the safety and tolerability of selumetinib in Chinese paediatric and adult subjects with NF1 and inoperable PN	 Paediatric and adult cohorts: Safety and tolerability will be evaluated in terms of AEs, clinical safety laboratory assessments, physical examination, vital signs, height/weight, ECG, echocardiogram, ophthalmologic assessment and performance status. Paediatric only: Safety and tolerability will also be evaluated in terms of bone growth and Tanner stages. 	
	Assessments related to AEs will include:	
	Occurrence/frequency.	
	• Relationship to IP as assessed by investigator.	
	CTCAE grade.	
	• Seriousness.	
	• Death.	
	• AEs leading to discontinuation of IP.	
	• AEs of special interest.	
To characterise the PK of selumetinib and its metabolite (N-desmethyl selumetinib) in Chinese paediatric and adult subjects with	PK parameters for selumetinib and N-desmethyl selumetinib will be derived following single dose and multiple doses. These may include, but are not limited to:	
NF1 and inoperable PN	After a single dose:	
	• AUC.	
	• AUC ₀₋₁₂ .	
	• AUC _{0-t} .	
	• C _{max} .	
	• t _{max} .	
	• t _{1/2} .	
	After multiple doses:	
	• AUC _{0-12,ss} .	
	• C _{max,ss} .	
	• Rac.	

Secondary objectives:	Endpoints:	
To evaluate the clinical efficacy of selumetinib in Chinese paediatric and adult subjects with NF1 and inoperable PN on ORR, DoR, PFS, TTP, and TTR	ORR is defined as the proportion of subjects who have a complete response or confirmed partial response (defined as a target PN volume decrease ≥20% compared to baseline, confirmed by a consecutive scan within 3 to 6 months after first response, as determined by the investigator and independent central review per Response Evaluation in Neurofibromatosis and Schwannomatosis (REiNS) criteria.	
	DoR is defined as the time from the date of first documented response (which is subsequently confirmed) until the date of documented progression or death in the absence of disease progression, as determined by the investigator and independent central review per REiNS criteria.	

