4.4 End of study definition

A subject is considered to have completed the study if he/she has completed all phases of the study including the last visit or last scheduled procedure as shown in Table 1.

Same DCOs would be applied for both analysis of pediatric cohort and adult cohort. Primary DCO in this study will take place when the last subject dosed has had the chance to complete their visit at the end of cycle 10. Final DCO will occur when the last subject dosed has had the chance to complete their visit at the end of cycle 24. In addition, an interim analysis will be conducted when last subject dosed has had the chance to complete their visit at the end of cycle 4 to assess PK, safety, tolerability and efficacy in Chinese subjects with NF1 and inoperable PN.

Subjects will be withdrawn from the study if the study is terminated. The study may be terminated if, in the judgment of AstraZeneca, study subjects are placed at undue risk because of clinically significant findings. In the event that a roll-over or safety extension study is available at the time of the final DCO and database closure, subjects currently receiving treatment with selumetinib may be transitioned to such a study, and the current study would terminate. The roll-over or safety extension study would ensure treatment continuation with visit assessments per its protocol. Any subject who would be proposed to move to such a study would be given a new ICF to sign.

If selumetinib is approved locally and reimbursed for use in paediatric/adult patients with NF1 who have symptomatic, inoperable PN, participants should be switched to the commercial supply at the end of the study. However, if the participant is unable to access the commercial supply and they are still receiving clinical benefit, AstraZeneca and the Investigator will discuss how the participant could continue to receive selumetinib if he/she is benefiting from treatment.

See Appendix A 6 for guidelines for the dissemination of study results.

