8.3.1 Method of detecting adverse events and serious adverse events

Care will be taken not to introduce bias when detecting AEs and/or SAEs. Open-ended and nonleading verbal questioning of the subject/care provider is the preferred method to inquire about AE occurrences.

8.3.2 Time period and frequency for collecting adverse event and serious adverse event information

All AEs, including SAEs, will be collected from the time the ICF (subject or parent/legal guardian) is signed, throughout the treatment period and up to the 30-day safety follow-up visit (30 days after the last dose of study treatment).

From the 30-day safety follow-up visit until the end of the long-term post-treatment safety follow-up visit:

- 1 All SAEs regardless of causality will be collected.
- 2 Only AEs considered causally related to selumetinib will be collected.

All SAEs will be recorded and reported to the sponsor or designee within 24 hours, as indicated in Appendix B. The investigator will submit any updated SAE data to the sponsor within 24 hours of it being available.

Investigators are not obligated to actively seek AEs or SAEs in former study subjects. However, if the investigator learns of any SAE, including a death, at any time after a subject's last visit and he/she considers the event to be reasonably related to the study treatment or study participation, the investigator may notify the sponsor.

The method of recording, evaluating, and assessing causality of AEs and SAEs and the procedures for completing and transmitting SAE reports are provided in Appendix B and Sections 8.3.5 and 8.4.1.

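### The final data cut-off leaves no time for the required 12-month paediatric safety follow-up, and a roll-over study would terminate the trial before some children complete it

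*Protocol*

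**What the plan says.** **Follow-up.** Footnote f to Table 1 (Section 1.1) states: "Long-term post-treatment safety follow-up assessments will be conducted for 1 year (at 6 and 12 months post-treatment) for paediatric subjects only". Sections 1.2 and 4.1 repeat this. Table 1 schedules height and weight, Tanner stage and performance status in that period. Section 8.3.2 continues collection of all SAEs and of related AEs over the same interval: "From the 30-day safety follow-up visit until the end of the long-term post-treatment safety follow-up visit". For the paediatric cohort, Table 2 (Section 3) makes growth and puberty part of the primary safety objective: "Safety and tolerability will also be evaluated in terms of bone growth and Tanner stages".

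**Final cut-off.** Sections 1.2, 4.4 and 9.5 tie it to one event: "Final DCO will occur when the last subject dosed has had the chance to complete their visit at the end of cycle 24". One cut-off serves both cohorts, and no time is added for follow-up.

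**Termination.** Sections 4.4 and 6.7 provide for a roll-over or safety extension study being available at the final cut-off and database closure. In that event "subjects currently receiving treatment with selumetinib may be transitioned to such a study, and the current study would terminate". Section 4.4 also says, without qualification: "Subjects will be withdrawn from the study if the study is terminated". If there is no such study, Section 6.7 lets subjects who benefit stay on selumetinib and recommends that they keep attending scheduled visits.

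**Completion.** Section 4.4 counts a subject as having completed the study only after the last procedure scheduled in Table 1. For a child, that includes the 12-month visit.

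**The concern.** Two stated rules conflict for one group: children who have permanently stopped selumetinib and are still within 12 months of stopping when the final cut-off arrives. Table 1 says their visits will be done. The roll-over clause ends the study, moves only subjects still on treatment, and gives these children no route to the remaining visits. By Section 4.4's own definition they would be withdrawn without having completed the study.

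If no roll-over opens, the same children can still be seen, but the protocol does not say how data collected after the final cut-off and database closure will be analysed or reported.

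At stake is post-treatment information on growth, puberty, SAEs and late related AEs. Among children who stop before the cut-off, those affected are the later stoppers, who will generally have had the longer exposure. In a cohort of about 16, one to three children is a noticeable share of that information.

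**Working it through.** **1. The plan's own figure.** Table 1 puts Cycle 1 Day 1 on study day 3, and dosing "will be administered continuously for 28-day cycles (starting at Cycle 1) with no rest periods between cycles". The end of Cycle c is therefore day 2 + 28c.
- Cycle 1: 2 + 28 = 30. Cycle 4: 2 + 112 = 114. Cycle 12: 2 + 336 = 338.
- Cycle 24: 2 + 672 = **674**.

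All agree with Table 1.

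**2. Latest end of treatment that allows full follow-up.** Let L be the number of days by which a child was dosed before the last subject in either cohort. On that child's own calendar the final cut-off is day 674 + L. The 12-month visit is reached only if treatment ended by day 674 + L − 365 = 309 + L.
- L = 0: day 309. Cycle 10 ends on day 282, so this is Cycle 11 Day 27.
- L = 86 (day 86 is the end of Cycle 3, about when the Safety Review Committee looks at the first 6 subjects): day 395, Cycle 15.
- L = 365: day 674, the end of Cycle 24.

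For the 6-month visit (183 days) with L = 0: 674 − 183 = day 491, in Cycle 18.

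So, whatever the enrolment pattern, a child who stops within 365 days before the cut-off has no 12-month visit in the final analysis. One who stops within about 183 days before it has neither visit.

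**3. How many children.** The protocol gives no discontinuation rate or enrolment pattern, so this step is illustrative. With a constant yearly discontinuation probability d, the chance that a child stops in the year before the cut-off is

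p = d × (1 − d)^((309 + L)/365).

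| d | p at L = 0 | × 16 | p at L = 365 | × 16 |
|---|---|---|---|---|
| 5% | 0.048 | 0.8 | 0.045 | 0.7 |
| 20% | 0.166 | 2.6 | 0.132 | 2.1 |
| 30% | 0.222 | 3.5 | 0.155 | 2.5 |

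Neither column is a realistic enrolment pattern, since each gives all 16 children the same L. A simulation with staggered entry assumed 6 children dosed over 90 days, an 86-day pause for the safety review, 10 more over 3 to 9 months, and d from 5% to 30%. The share stopped but cut short was 0.05 to 0.20 of the cohort: 16 × 0.05 = 0.8 to 16 × 0.20 = 3.2, or about 1 to 3 children. That is 32% to 46% of the children who had stopped by the cut-off.

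**4. What the text does with these children.**

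| At the final cut-off | Child still on treatment | Child off treatment for under 12 months |
|---|---|---|
| Roll-over available | May transfer | Transfer clause does not apply; study terminates; subject withdrawn |
| No roll-over | May continue treatment and visits | Visits can still occur; no analysis of them stated |

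**The case against.** The strongest reply is that the protocol cancels nothing at Cycle 24. Only the cut-off is fixed there, and termination needs a roll-over study that may never exist. Treatment runs until progression or unacceptable toxicity, so any fixed cut-off leaves some follow-up unfinished. Other provisions soften the loss. Section 8.2.9 has children with impaired growth velocity followed to final adult height. Section 8.3.3 has follow-up information on ongoing SAEs reported after database lock. Appendix A 9 asks that subjects' interests be protected on termination. The withdrawal sentence in Section 4.4 also stands beside text on termination for undue risk and may have been written with that in mind.

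Much of this stands, and it limits the point. It does not settle the position of off-treatment children under a roll-over. The withdrawal sentence is not confined to safety-driven termination, and none of these provisions replaces the scheduled 6- and 12-month visits.

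Four stronger readings are tempting but unsupported:
- **That the study itself ends at the Cycle 24 visit.** Termination is conditional on a roll-over; otherwise Section 6.7 foresees continuation.
- **That the 6- and 12-month visits are the only look at growth and puberty after stopping.** Table 1 also schedules height, weight and Tanner stage at the 30-day visit.
- **That most of the cohort loses follow-up.** Under the assumptions above, 61% to 94% of children could not have a 12-month visit by the cut-off, but most of them are still on treatment and have no post-treatment visit due.
- **That the timetable is unworkable.** The Synopsis gives "Estimated date of last subject completed: Q4 2023". Setting this against a last-dosed child who stops exactly at Cycle 24 and then needs 365 more days compares a worst case with a date that is only an estimate.

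The primary safety analysis is also largely intact. On-treatment growth, Tanner and AE data and the follow-up of earlier stoppers are all included, and treatment-emergent AEs end 30 days after the last dose in any case (Section 9.5.2).

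**Conclusion.** The point holds as a gap between stated rules. The final cut-off makes no allowance for the required paediatric follow-up. If a roll-over study is available, the text as written withdraws off-treatment children before visits that it elsewhere says will be done. If none is available, the visits can go ahead but those after the cut-off have no stated analysis.

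The timing result (day 309 for the last subject dosed, and any stop within 365 days before the cut-off for everyone) follows from the protocol's own calendar and needs no assumption. The count of about 1 to 3 of 16 children rests on the assumed enrolment pattern and 5% to 30% yearly discontinuation. On the document alone it could be anywhere from 0 to 16. It also takes a child as the last subject dosed. If an adult is last, L rises for every child and the figure falls somewhat, as the L = 365 columns show.

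This is a modest but worthwhile correction: few children, a contingent trigger, and a cheap remedy.

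**What to change.** In Sections 4.4 and 6.7, reconcile the termination wording with Table 1. State that neither the final cut-off nor a roll-over terminates the study for paediatric subjects who have permanently stopped treatment until their already required 12-month visit. State also that data from these visits after the final cut-off will be reported in an addendum to the final clinical study report.

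The final cut-off and the main final analysis stay where they are, and no visit or procedure is added. The cost is amendment wording, a short safety addendum, and a formal study end up to 12 months later for a few children.

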4.5 Safety Review Committee

An SRC will be established to perform a review of the safety, tolerability and PK (if available) of selumetinib treatment in this study.

The core members of the SRC consist of:

- Study physician, who will chair the committee, or delegate.
- Principal investigator or delegate from each investigational site that participates in the study.
- Global/local safety physician or delegate.
- Global clinical lead.

In addition, the study pharmacologist, study statistician and global study leader may also be invited as appropriate.

A separate document or remit will define the exact membership, role and responsibility (SRC charter).

Within each cohort, the SRC will evaluate preliminary tolerability, safety and available PK data after the first 6 subjects have been treated for approximately 3 cycles. Additional enrolment will be initiated per SRC recommendation. If necessary, further safety review committee meetings will be held. Detailed information will be provided in the SRC charter.

CONFIDENTIAL AND PROPRIETARY 41 of 183

5. STUDY POPULATION

Subjects will be enrolled in China. Chinese subjects with a clinical diagnosis of NF1 (NIH Consensus Development Conference Statement 1988) and inoperable PN that require treatment due to symptoms or with the potential to develop significant clinical complications, as judged by the investigator, will be eligible.

Approximately 16 paediatric and 16 adult subjects with NF1-related and inoperable PN are expected to be recruited.

Prospective approval of protocol deviations to recruitment and enrolment criteria, also known as protocol waivers or exemptions, are not permitted.

Each subject should meet all of the inclusion criteria and none of the exclusion criteria for this study in order to be enrolled. Under no circumstances can there be exceptions to this rule. Subjects who do not meet the entry requirements are screen failures (refer to Section 5.4).

For procedures for withdrawal of incorrectly enrolled subjects, see Section 7.3.

